9.3 Relationship of AE to Study

The relationship of each adverse event to the study procedures will be characterized. The PI will make this determination and will classify adverse events as related or unrelated. "Related" will mean that there is a reasonable possibility that the AE may be related to the study agent(s). "Not Related" will mean that there is not a reasonable possibility that the AE is related to the study agent(s). When a SAE is assessed as "not related" to study agent, an alternative etiology, diagnosis, or explanation for the SAE should be provided. If new information becomes available, the relationship assessment of any AE should be reviewed again and updated, as required. The study drug which a participant has taken will be assessed for relationship with the AE.

9.4 Reporting of Serious Adverse Events, and Unanticipated Problems

The DAIDS-assigned Medical Monitors will be alerted to any new Grade 3 or Grade 4 AEs in real time via email. This is in addition to the formal AE reporting requirements below.

Requirements, definitions and methods for expedited reporting of adverse events are outlined in Version 2.0 of the DAIDS EAE Manual, which is available on the DAIDS RSC website at

<https://rsc.niaid.nih.gov/clinical-research-sites/manual-expedited-reporting-adverse-events-dails>. This study will use the SAE form of expedited adverse event reporting, as defined in Version 2.0 of the DAIDS EAE Manual. The study product for which expedited reporting is required is imatinib. The EAE reporting period for this study will be 42 days, which is the day of the final study visit. During these 42 days, all SAEs will be reported to DAIDS in an expedited fashion, within 3 days of occurrence, in accordance with DAIDS EAE Manual. The study drug a participant has taken (imatinib) will be assessed for relationship with the SAE. In addition to the SAE Reporting Category identified above, other AEs that must be reported to DAIDS in an expedited manner are:

- Any gastrointestinal or liver toxicity of grade 3 or higher
- Any uveitis of grade 2 or higher
- Episodes of ventricular tachycardia or fibrillation, syncope, and seizure
- Grade 3 or higher QTcF prolongation
- Any Grade 4 event, including laboratory values
- Heart failure of grade 3 or higher

After the protocol-defined EAE reporting period, unless otherwise noted, only SUSARs as defined in Version 2.0 of the DAIDS EAE Manual will be reported to DAIDS if the study staff become aware of the events on a passive basis (from publicly available information). Of note, although pregnancy is not an AE, all pregnancies that occur during the study will be reported to DAIDS given the teratogenic potential of imatinib. Any pregnancy occurring during the study will be followed to assess any negative outcomes resulting from exposure to the study drug. Reporting of pregnancies will not use the EAE system, but will be include a written clinical summary of the pregnancy including but not limited to the date discovered, any study or other medications taken during the pregnancy period, the expected due date, and eventual outcome. Pregnancies will be reported to DAIDS first within 7 business days after discovery, and monthly reports will follow until the end of the pregnancy period.

The DAIDS Adverse Experience Reporting System (DAERS), an internet-based reporting system, must be used for EAE reporting to DAIDS. At least two staff members at the Emory site will have a combination of Reporter and Submitter rights to DAERS. In the event of system outages or technical difficulties, EAEs may be submitted using the DAIDS EAE Form. This form is available on the DAIDS RSC website at

<https://rsc.niaid.nih.gov/clinical-research-sites/paper-eae-reporting>.

For questions about DAERS, please contact NIAID CRMS Support at [contact]. Please note that site queries may also be sent from within the DAERS application itself. For questions about expedited reporting, please contact the DAIDS RSC Safety Office at ([contact]).

Written Investigational New Drug (IND) safety reports will be submitted to the FDA using FDA Form 3500A by DAIDS, for SUSARs within 15 calendar days of DAIDS determining that the information requires reporting. If the event is fatal or is deemed to be life threatening, the report will be made within 7 calendar days. The Investigator will also make an assessment of whether the event constitutes an unanticipated problem posing risks to participants or others (UP). This assessment will be provided to the Emory University IRB and DAIDS, which, in turn, will make a final determination. If the Emory IRB determines an event is a UP it will notify the appropriate regulatory agencies and institutional officials.

The Investigator is responsible for reviewing all IND Action Letters, Safety Reports and any other safety related Investigator Notifications and determining the action to be taken (i.e. prompt reporting to the IRB, consent change/modification, routine reporting, etc).

Co-investigators and the Investigator must conform to the adverse event reporting timelines, formats and requirements of the various entities to which they are responsible. In narrative reports, the minimum necessary information to be provided at the time of the initial report includes:

- Study identifier
- Participant number
- A description of the event
- Date of onset
- Current status
- Whether study intervention was discontinued
- The reason why the event is classified as serious
- Investigator assessment of the association between the event and study intervention

9.4.1 Follow-up report

If an AE has not resolved at the time of the initial report and new information arises that changes the Investigator's assessment of the event, a follow-up report including all relevant new

or reassessed information (e.g., concomitant medication, medical history) will be submitted to the IRB. The Investigator is responsible for ensuring that all AE are followed until either resolved or stable.

9.5 Medical Monitoring and Toxicity Management

[name] is a Professor of Hematology and Oncology with extensive experience administering imatinib to CML patients at Emory University Hospital. She is certified by the American Board of Internal Medicine in Hematology. She will serve as the Independent Safety Monitor (ISM) for this study. [name] role will be to help monitor the safety of participants and adjudicate adverse events that may be related to imatinib. She has 9 years of experience as principal and co-investigator on multi-institutional clinical trials including trials evaluating transplantation for adults with acute leukemia. These collaborations have led to peer reviewed publications in high impact journals, such as *The Journal of Clinical Oncology*, *Cancer*, and *Lancet Oncology*. Her strong background in clinical investigation and experience as member, and now as vice chair of the Winship Data and Safety Monitoring Committee, make her exceptionally qualified to serve as the Independent Safety Monitor for the trial. The monitor will attest to the absence of relevant conflicts of interest as defined by NIAID and will be approved by all relevant regulatory bodies prior to beginning the study.

The ISM and the PI/co-PI will review safety data as enrollment progresses, assessing AE summaries in real-time and formally on a weekly basis for clinical significance and facilitating attribution to study medication (protocol [Section 9.2](#) and [Section 9.3](#)). The ISM will provide information to the DSMB on frequency and severity of AEs.

For individual toxicity management, the PI will review all toxicity reports of grade 2 or higher in real time in order to decide on possible need for intervention or drug discontinuation. In general, a grade 2 AE thought to be related to a study drug that does not respond to non-pharmacologic intervention (e.g., salt restriction and elevation of legs for pedal edema) will lead to consideration for drug discontinuation, and any grade 3 or higher AE will cause discontinuation of study drug. Participants taken off study drug will be followed for safety if willing but will not participate in PK studies.

For manual differential ALC and ANC lab values classified as Grade 3 - Grade 4 AEs, the study team will request that the Emory Medical Lab re-check the counts using the same specimen.

This will provide the needed confirmation of the low count, or indication that the first count was a lab error, allowing the team to make better informed action decisions.

Plans for treatment of common side effects of imatinib are listed below, including symptom grading that warrants drug discontinuation.

The following 4 side effects / AEs will be graded using the FDA Guidance Document, "Toxicity Grading Scale for Healthy Adult and Adolescent Volunteers Enrolled in Preventive Vaccine Clinical Trials Guidance for Industry," September 2007.

- Low blood counts: Monitor blood counts more frequently for grade 1-2 leukopenia, anemia or thrombocytopenia. Discontinue study drugs if grade 3 or higher.
- Nausea and vomiting: Treat symptomatically with OTC medications for grade 1-2. Discontinue study drugs if grade 3 or higher.
- Diarrhea. Treat symptomatically with OTC medications for grade 1-2. Discontinue study drugs if grade 3 or higher.
- Fever: Treat symptomatically with OTC medications for grade 1-2. Discontinue study drugs if grade 3 or higher.

The following 3 side effects will be graded using the Division of AIDS (DAIDS) Table for Grading the Severity of Adult and Pediatric Adverse Events - Corrected Version 2.1, July 2017

- Skin rash (skin reactions): Treat symptomatically with OTC medications for grade 1. Discontinue study drug if grade 2 or higher.
- Muscle cramps and bone pain. Treat symptomatically with OTC medications for grade 1. Discontinue study drug if grade 2 or higher. See "Pain (not associated with study agent injections and not specified elsewhere)," Page 21 of the DAIDS AE Grading Table.
- Hemorrhage (bleeding problems): Grade 1, N/A. Discontinue study drug if grade 2 symptoms or higher, or decrease in Hgb > 1.5 g.

Edema is not listed in the FDA Guidance document or the DAIDS table, and will be graded using the Common Terminology Criteria for Adverse Events (CTCAE) Version 5.0, Nov 2017.

- Edema (swelling of the face, feet, hands): Treat symptomatically with salt restriction and limb elevation if possible for grade 1-2. Discontinue study drug if grade 2 edema does not respond to non-pharmacologic treatment, or for higher grade edema.

9.5.1 Study Progress and Safety Monitoring Plan

The Division of AIDS guidance on study monitoring have been implemented to develop a protocol-specific Study Progress and Safety Monitoring Plan (SPSMP), which will be approved

in writing by the assigned DAIDS Medical Monitor/Medical Officer before trial initiation. Briefly, the ISM, DAIDS representative, and the PI/study team will review all reports at least monthly, with AE reports generated every 2 weeks. The following reports will be generated: 1) Accrual update, 2) Progress report, 3) Delinquency report, 4) Periodic summary adverse event report, 5) Baseline characteristics report, 6) Data completeness report, 7) Outcomes summary report (completed, withdrew, etc), 8) Efficacy report (myelopoesis). The contents of the report will be as outlined in the DAIDS SPSMP protocol template, which can be found at: (https://www.niaid.nih.gov/sites/default/files/studydatamonitor_plan.pdf) and which has been used to create a study-specific SPSMP. The reports created for this process will be provided to DAIDS at the frequency of each review as specified in the SPSMP. The DSMB will receive these reports at the planned imatinib dose group 6- and 12- participant completion points as described in [Section 3.1.2.](#)

A DAIDS-appointed study monitoring team will provide oversight and monitoring for the conduct of this study. This DAIDS-appointed team will conduct study-monitoring functions to ensure that the research produces high-quality scientific data in a manner consistent with good clinical practice (GCP) and appropriate regulations that govern clinical research. We expect that this trial will be risk classified by the scientific review committees as Moderate Risk, based on the history of use in healthy volunteers and the known adverse event profile and doses of the agents used. For studies deemed Moderate Risk, initial monitoring occurs within 1 year from the date of the first participant accrued, with 2 of the first 5 participants being reviewed. For this trial, this approach will apply to each imatinib dose cohort. The monitor(s) will review all aspects of the study, with a primary goal of assessment of participant safety, as well as compliance with the protocol, data collection, and risk-benefit ratio. Specifically, the monitor(s) assigned by DAIDS may verify informed consent, eligibility, data entry, accuracy and availability of source documents, AEs/SAEs, and essential regulatory documents. The monitor(s) will then prepare a final monitoring summary report.

[name] and the investigators, the ISM, the clinical research coordinator and the regulatory affairs coordinator will meet at least monthly to review and discuss study data to ensure participant safety. During the meetings the PI or co-I will review the eligibility criteria for each new participant. In addition, during these meetings the group will review all adverse events, random checks of case report form completion and a roadmap for each participant on the trial.

All study personnel will be trained on the protocol by the PI or co-I. Study personnel will sign the training log prior to being included on delegation of authority log. All adverse events will be handled according to [Section 9.4](#), which provides detailed instructions on reporting requirements.

The PI and the ISM will formally review clinical toxicity assessments with the DAIDS medical monitor every two weeks and after 6 participants have completed follow-up in a dose stratum. The PI and/or medical monitor will halt further enrollment at that dose level for formal review by the DSMB if any participant develops any emergent grade 3 or higher dose-limiting toxicity that is definite, possible or probable in causal relationship to the study drug, in the opinion of the PI. If no such toxicity is observed after the first 6 participants in a dose stratum have completed follow-up, and a total of 12 participants are enrolled in the first stratum, then the next dose stratum will be opened for enrollment.

The safety rationale for opening accrual to a higher dose level, based upon findings from the first 6 participants at the previous lower dose level, is as follows: Rather than use a standard 3 + 3 dose escalation design, we will utilize a more conservative threshold for halting accrual. In this study, enrolling healthy volunteers, a frequency of >33% grade 3 or higher dose-limiting toxicity attributed to a study drug would warrant formal review by the DSMB. We propose to protect participant safety by performing a safety analysis after 6 participants have completed the day 42 follow-up visit, a sample size that gives us greater than 90% power to identify a safety signal and halt accrual at that dose level, based upon a true rate of grade 3 or higher toxicity of 33% (or greater).

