The primary outcome is the change in the numbers of myelomonocytic cells in the blood between baseline and day 14 of the study. The change in these cells will be estimated with mixed models, combining all dose groups, with interactions between dose and each time point. Secondary efficacy analyses will also use mixed models to determine the relationship between imatinib exposures and change in the numbers of myelomonocytic cells at each dose separately and in the pooled dose strata. Similar analyses will be used to assess bacillary killing, as determined by the Whole Blood Bactericidal Assay (WBA), using bacille Calmette-Guerin (BCG), at day 14.

Safety

The incidence of all adverse events and in particular grade 3 or 4 adverse events and SAEs during all follow-up time will be determined using point estimates and 95% CIs.

Pharmacokinetic analysis

Pharmacokinetic (PK) parameters, including absorption, distribution, and metabolism, will be determined using S-ADAPT software utilizing a compartmental PK analysis approach and summarized by treatment regimen.

Study design

Dose-escalation trial with PK components

Power and Sample Size Analysis

At completion of the study, 48 participants with evaluable data will provide 90% power to detect a 0.48 SD in the change in the number of myelomonocytic cells on imatinib. Within each dose stratum, we will have 90% power to detect a 1.03 SD change.

Safety Evaluations

Clinical and laboratory adverse events including ECG changes will be monitored prospectively while on study drug and at 14 days after completion of imatinib.

Study Progress and Safety Monitoring Plan

The Independent Safety Monitor, PI and study team, Data Safety Monitoring Board (DSMB), and Sponsor will be responsible for monitoring the data quality and the ongoing safety of participants. Twelve participants will be enrolled into each dosage arm in an ascending manner, starting with the 100 mg imatinib dose. A safety analysis will be performed by the team and the DSMB after complete safety data are available from 6 participants within a stratum. If safe, and after a total of 12 participants are enrolled for the first stratum, then the next higher dose will begin enrolling participants. Enrollment will proceed in this manner until the sample size has been reached. Formal safety analysis will then occur using the data from all dose groups.

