3.1.2 Study Intervention Phase

The doses of imatinib used here are the same or lower than those used routinely and safely in CML patients, and we do not expect any Grade 3 or Grade 4 adverse events (AEs). Hence, safety evaluations for this imatinib-only amended protocol will consist of e-mailed adverse event reports to DAIDS, followed by communication from DAIDS to the DSMB. Any Grade 3 or Grade 4 adverse events will be reported to DAIDS in real time.

We will enroll using a sequential dose-escalation design. Specifically, we will enroll 2 more participants in the imatinib 100 mg qD arm, which brings enrollment in this group to 6 participants. We will conduct a safety review of adverse events after these 6 participants given imatinib 100mg complete day 42 follow-up. Enrollment of the second 6 participants in the 100mg dose group will continue while safety review of the first 6 participants is conducted by the DSMB via e-mail. The plan to continue enrollment during this review period is based on the known safety profile of imatinib in CML patients who take 400 to 800mg daily. If after the first 6 participants at 100mg complete the 42-day study follow-up there are no treatment emergent grade 3 or 4 adverse events considered to be related to imatinib treatment, and there are no serious adverse events or other safety concerns among these first six volunteers as well as volunteers 7 - 12 in the opinion of the investigators, the Independent Safety Monitor, the DSMB,

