and the Sponsor that would prevent dose escalation (also documented through e-mail communication), we will commence enrollment of the 12 participants in the next dose group (200mg qD arm). We will again conduct a safety review of adverse events via e-mail after the first 6 participants in the group complete day 42 followup while continuing with the next 6 participants in the group as above, following the same procedures before starting the 400mg imatinib group. After 6 participants complete day 42 followup in the 400 mg qD arm, we will review safety data and PK/PD data while enrollment in the 400 mg/day group continues. If the safety criteria above are met, we will complete enrollment of remaining participants in the 400 mg qD arm. This approach will proceed until there are 12 participants with evaluable myelopoiesis data in each dose arm and the sample size of 48 participants (16 in the previous protocol version plus 32 in this version) is fulfilled. All enrolled participants will be evaluable for safety and toxicity assessments if they have taken at least one dose of a study drug. Note that in this protocol version, given imatinib dosing only occurs for 28 days, 42-day followup is required for a participant to “count” toward the 6 needed for followup assessment. Therefore, if any of the first 6 participants in a dose group do not complete the study to day 42, we will need to include other participants who complete the day 42 visit to fulfill the requirement. Similarly, because study endpoints require data collection up to day 14, if a participant drops out prior to day 14, we will enroll another participant to complete the required complement of 12 participants with protocol-compliant evaluable data (has taken $\geq 85\%$ of all doses of study drugs and completed visits to day 14) per dose group (see [Section 8.1](#) and [Section 8.2](#)).

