8.1.2 Interim Analysis

Given imatinib is an FDA-approved drug with a known safety profile, we expect the doses used in this study to be well tolerated. After the first 6 participants in the 200mg dose group have completed the day 28 follow-up visit, the study team, the Data Safety Monitoring Board (DSMB),

the Independent Safety Monitor, and the Sponsor will evaluate the safety data and determine via email whether it is safe to proceed to enrolling in the 400mg dose group after the previous group is fully enrolled. Note that since 42-day follow-up is required for a participant that “counts” toward the 6 needed for follow-up safety analysis, if any of the first 6 participants in a dose group do not complete the study to day 42, we will need to include other participants who complete the day 42 visit in order to fulfill the requirement.

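### Version 5.0: the toxicity halt covers only the dose level where the event occurs, so it does not pause an already open doubled dose, and the 200-to-400 mg gate is dated both day 28 and day 42

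*Combined protocol and SAP*

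**What the plan says.** All references are to Version 5.0 unless stated.

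- **Halt.** Section 9.5.1 tells the PI and/or medical monitor to "halt further enrollment at that dose level for formal review by the DSMB if any participant develops" a related, emergent grade 3 or higher dose-limiting toxicity.
- **Opening the next dose.** The same section says that if the first six complete follow-up without such toxicity and "a total of 12 participants are enrolled in the first stratum, then the next dose stratum will be opened for enrollment". The Study Summary agrees: "after a total of 12 participants are enrolled for the first stratum, then the next higher dose will begin enrolling participants". Section 3.1 likewise speaks of complete enrolment, not complete follow-up. Each step doubles the dose (100 to 200 to 400 mg).
- **Volunteers 7-12.** Section 3.1.2 makes escalation conditional on the judgement that "there are no serious adverse events or other safety concerns among these first six volunteers as well as volunteers 7 - 12", with no minimum follow-up for the second six. Section 12.1 requires a DSMB recommendation before each step.
- **Replacements.** Section 3.1.2 also provides that "if a participant drops out prior to day 14, we will enroll another participant to complete the required complement of 12 participants".
- **Reports.** Section 9.5.1 states: "The DSMB will receive these reports at the planned imatinib dose group 6- and 12- participant completion points as described in" Section 3.1.2. Section 9.4 has grade 3 and 4 events e-mailed to the medical monitors in real time.
- **200-to-400 mg gate.** Section 8.1.2 places the decision "After the first 6 participants in the 200mg dose group have completed the day 28 follow-up visit". Its next sentence requires 42 days for a participant to count, and Sections 3.1.2 and 9.5.1 also say day 42. Day 28 is the last dosing day (Section 6.2.7).

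**The concern.** The halt is meant to keep people from starting a drug when a related severe event has occurred. Once the next dose is open, the lower stratum has its 12, so a halt confined to that level can stop only replacement enrolment there. The people about to start drug are at the higher dose, and the written rule does not reach them. They are healthy volunteers, and Section 12.1 says imatinib toxicity is dose-related, so a related event at the lower dose bears directly on them.

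The second six matter most at the 100-to-200 mg step. The first six there are four participants from the earlier version plus two new ones (Section 3.1). Under the earlier regimen, rifabutin and isoniazid were added after day 14. If the four followed it, only eight participants take 100 mg alone past day 14, and volunteers 7-12 are six of those eight.

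The day-28 wording is a separate defect. Read literally, it drops the 14-day post-drug follow-up before escalation to the highest dose.

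**Working it through.** **The plan's own figure.** Section 9.5.1 claims more than 90% power to detect a signal in six participants at a true rate of 33%. Under the any-participant trigger this is 1 − 0.67^6 = 0.9095, so it reproduces. The gate of six completers is not questioned here.

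**Whether the gap exists.** This follows from the text: opening requires 12 enrolled, the halt is limited to the level of the event, and no sentence extends it. It applies at 100 and 200 mg only, because no dose lies above 400 mg.

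**How often it would matter.** Version 5.0 gives neither accrual rate nor review time, so both are assumed. The rates used are 1 per week and 3 per week (the latter is an example in Section 3.1.2 of Version 3.0), with a gate review of 0 or 2 weeks.

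- First enrolment is day 1; spacing is 7 or 7/3 days.
- Opening day = the later of (day-42 visit of participant 6 + review) and (enrolment of participant 12). At 1 per week, participant 6 enrols on day 36 and reaches day 42 on day 77; participant 12 enrols on day 78.
- E = days remaining to day 42 at opening, summed over volunteers 7-12, divided by 42.
- With per-person rate p and constant hazard to day 42, the chance of a clean stratum up to opening and then at least one event in 7-12 is (1−p)^(12−E) − (1−p)^12.

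| Scenario | Opens on day | Study days of 7-12 at opening | Days left | E | p=5% | p=10% | p=20% |
|---|---|---|---|---|---|---|---|
| 1/week, no review | 78 | 36, 29, 22, 15, 8, 1 | 141 | 3.36 | 10.2% | 12.0% | 7.7% |
| 1/week, 2-week review | 91 | 49, 42, 35, 28, 21, 14 | 70 | 1.67 | 4.8% | 5.4% | 3.1% |
| 3/week, no review | 53.7 | 39.7 down to 28 | 49 | 1.17 | 3.3% | 3.7% | 2.0% |
| 3/week, 2-week review | 67.7 | 53.7 down to 42 | 0 | 0 | 0% | 0% | 0% |

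Example (second row, p = 10%): 0.9^10.33 − 0.9^12 = 0.3366 − 0.2824 = 0.054. The figures fall at 20% because a high rate usually fails the gate first.

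If hazard is confined to the 28 dosing days, the remaining dosing days are 66, 21, 0 and 0. Then E = 2.36, 0.75, 0 and 0, and at p = 10% the chances are 8.0%, 2.3%, 0% and 0%.

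**What a pause would save.** It spares those due to start while the DSMB reviews the event: weekly accrual × weeks of review. At 1 per week with 2-week reviews, that is 2 starts if the event occurs, so 0.054 × 2 ≈ 0.11 per step (0.023 × 2 ≈ 0.05 with hazard confined to dosing). In a simulation of 400,000 strata (p = 10%, hazard to day 42), an average of 2.5, 2.0 and 2.6 volunteers had already started the higher dose before the event in the first three scenarios. A pause on enrolment does not help them.

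**Day 28 against day 42.** With a day-28 gate, opening falls on day 78, 78, 39.7 and 53.7, which is 0, 13, 14 and 14 days sooner. The same formula at p = 10% (hazard to day 42) then gives 12%, 12%, 11% and 4%, against 12%, 5%, 4% and 0%. It still requires the first six to be clean to day 42, which is stricter than a day-28 gate.

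**The case against.** The best case against rests on what the file does not show and on how little is gained.

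- **The unseen plan.** The DAIDS template was "used to create a study-specific SPSMP", which is not in the file and may already contain the pause. This stands as a limit.
- **The 12-participant report.** If the 12-participant completion point means completed follow-up before escalation, the window closes. That reading is possible, but the Study Summary and Sections 3.1 and 9.5.1 all make enrolment the condition.
- **Other safeguards.** The halt sentence triggers formal DSMB review, grade 3 and 4 events are alerted in real time, and the DSMB or sponsor could pause the higher dose at discretion. All true, but none obliges anyone to pause. The DSMB recommendation and the check on volunteers 7-12 act before escalation.
- **Size.** The benefit is near 0.1 starts per step in a middling scenario, over only two steps. At 3 per week it is zero with a 2-week review, and zero at any review time if hazard is confined to dosing. Section 3.1.2 expects no grade 3 or 4 events. This stands, and the point should not be argued on probability.
- **The 100-to-200 mg step.** Four of its 12 participants are historical, so their outcomes are already fixed and the per-step figures are inexact there. That they took rifabutin and isoniazid is inferred from the earlier regimen. Neither fact affects the gap or the fix.
- **Section 8.1.2.** It could be called an editorial slip that corrects itself in the next sentence. But it is the stated time of a dose-escalation decision, and two different days cannot both govern it.

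**Conclusion.** Both parts hold on the Version 5.0 text. As written, a related grade 3 or higher event in volunteers 7-12 after escalation brings DSMB review but no required pause at the doubled dose. The 200-to-400 mg gate carries two inconsistent dates.

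At an assumed 10% event rate, the first gap arises with a chance of 0% to 12% per step, and the expected number of starts spared is about 0.1 or less at one enrolment a week with two-week reviews. These figures depend on assumed accrual, review time, event rate and hazard shape. The case for acting rests on whom the rule covers and on the very low cost of correcting it. This should be fixed. Confidence is medium, mainly because the study-specific monitoring plan could not be seen.

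**What to change.** 1. In Section 9.5.1, extend the halt beyond the affected level by adding: *and at any higher dose level already open, until the DSMB has reviewed the event and recommended resuming*. If the study-specific monitoring plan already contains this rule, a cross-reference is enough.
2. In Section 8.1.2, change day 28 to day 42.

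The gate of six completers and 12 enrolled stays as it is. Both changes fit in a letter of amendment and add no participants, visits or samples. The first delays accrual only if such an event occurs, and only for the length of the DSMB review. The second costs nothing against the day-42 rule stated elsewhere. Against the literal day-28 reading it costs 0, 13, 14 or 14 days in the four scenarios.
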